6 STUDY INTERVENTION

6.1 STUDY INTERVENTION(S) ADMINISTRATION

6.1.1 STUDY INTERVENTION DESCRIPTION

Transcranial Direct Current Stimulation (tDCS):

tDCS will be delivered to the study subjects through two electrodes ($5 \times 7 = 35 \text{ cm}^2$) via a direct current delivery device. In the bihemispheric montage, the anodal electrode will be placed over the ipsi-lesional and the cathodal electrode over the contra-lesional motor cortex (C3 and C4 using the international 10-20 EEG electrode systems). Electrode pads will be disposed after each week or 5 sessions. Pads will not be shared across subjects. Stimulation will last for 30 minutes (± 6) minutes for each session. Subject will receive either sham, 2 mA or 4 mA. Records of current will be checked and kept separately without unbinding the sites.

mCIMT:

The mCIMT protocol in this study is adapted from a protocol published in the EXCITE and VECTOR trials^{14, 19}. The premise of the strategy is that repetitive object grasping and manipulation practice reduces the effects of “learned non-use.” mCIMT will be delivered 120 minutes (\pm 24) minutes a day (with the first 30 minutes (\pm 6) minutes simultaneously with tDCS stimulation) for 10 sessions over 2 weeks with the unaffected arm in a constraining mitt for at least 6 hours/day during waking hours. Subjects will not be allowed to use the constrained hand within the task effort. The tasks attempted during the therapy session will be menu driven. Activities will be selected from a task menu, and an activity log kept demonstrating what tasks have been attempted. Each activity will be carried out for 15-30 minutes and activities selected should be challenging yet feasible for the subject, contextually appropriate (i.e., with regards to interests) and challenge movements that need improvement.

Training will primarily consist of task practice (TP) activities designed to promote increased use of the affected upper extremity during functional activities. These activities simulate activities of daily living (ADL) and instrumental activities of daily living (IADL), i.e., common daily activities. If a subject is unable to perform TP activities, the trainer may select activities from a menu of adaptive task practice (ATP) activities. ATP activities are comprised of the basic units or components of larger activities employed in TP. ATP activities focus on improving skills such as grasp, manipulation, dexterity, gross motor control, endurance, timing, and active range of motion. Whenever possible, ATP should be transitioned into TP activities as the subject’s skill level increases. The subjects will be provided with feedback (specific knowledge of results about a subject’s performance over a session); coaching (suggestions verbally to improve performance); modeling (physically demonstrate a task with the purpose of improving a subject’s performance); and encouragement (providing motivation to subjects verbally to promote maximal effort). Patients will wear the mitt for at least 6 hours of waking hours at home. Behavioral techniques to enhance mitt use outside of the research laboratory will include the use of a behavioral contract daily schedule, and encouragement from the supervising therapist to practice 2 to 3 specific tasks daily at home. A behavior contract will be provided to the subject at the end of the first intervention session.

6.1.2 DOSING AND ADMINISTRATION

Subjects will be 1:1:1 randomized to sham, 2 mA, or 4 mA group. Investigator, therapist and the subject will not be informed of the group assignment. All subjects will be prepared in the same way. tDCS will be executed by entering WebDCU-generated code in the computer, which will initiate one of the three interventions according to the group to which the subjects was randomized: sham, 2 mA or 4 mA. Thirty minutes of tDCS (including sham) will be accompanied by 120 (\pm 24) minutes of mCIMT with both starting at the same time, overlapping for the first 30 (\pm 6) minutes, and leaving the remaining 90 minutes for mCIMT only. tDCS is delivered by a small, battery-operated device, portable (e.g., can be mounted to a belt) and it does not interfere with mCIMT.

6.2 PREPARATION/HANDLING/STORAGE/ACCOUNTABILITY

6.2.1 ACQUISITION AND ACCOUNTABILITY

In order for a new medical product to reach patients, it must first be proven safe and effective and then be approved for use by the governing regulatory body. Clinical trials are the vehicle to bring these innovative technologies to subjects and evaluate them in support of regulatory approval. In clinical research the products are still investigational, these products are treated differently than

those items used in general medical practice. After all, using an unapproved product that is not fully vetted for safety and efficacy outside of the trial protocol requirements could result in risks to subjects.

Failure to account for and manage study materials could affect the acceptability of the data collected from a trial, or even termination of a study completely. Both sponsors and investigators have responsibility for device accountability and can be held accountable if problems are identified.

Accountability:

- The site investigator is responsible for the investigational product/device accountability at the trial site
- The site investigational product/device should be stored in accordance with the applicable regulatory requirements.
- The site investigator should ensure that the investigational product/device are used only in accordance with the approved protocol.

6.2.2 PRODUCT STORAGE AND STABILITY

The device should be accessible by the study team only. The device, including the battery, wires, and electrode pads will be checked before and at the end of each session. Each site will be dispensed with two tDCS systems (one for use and another for backup). Any issue should be reported immediately to the site investigator and further to the tDCS core team

6.2.3 PREPARATION

tDCS core personnel will prepare and test the tDCS system before dispensing to the site staff. The site staffs will attend a required onsite training workshop to gain knowledge how to operate the tDCS system.

6.3 MEASURES TO MINIMIZE BIAS: RANDOMIZATION AND BLINDING

On the randomization day, a study coordinator or a team member will log into WebDCU™ to randomize subjects who have been consented and found eligible. Briefly, at the beginning of each intervention session, the coordinator will complete tDCS Treatment Activation Code Request to obtain a new tDCS treatment activation code daily. Each day, the coordinator will need to enter the new code into the tDCS machine which will translate the code to the appropriate stimulation voltage using a pre-loaded script (**Fig 8, right**). The treating therapist is only to conduct mCIMT on the study subject, another study team member should conduct concurrent tDCS stimulation session to avoid potential bias.

Subjects will be allocated equally among the three treatment arms using a covariate adaptive randomization algorithm which controls for serious imbalances in covariates considered to have an impact

[figure not shown]

Fig 8. Schematic of interface between tDCS control, dual-channel tDCS delivery system, and WebDCU™ interface.

on outcome; specifically, study site, time from stroke, and baseline motor impairment measured using FM-UE scale. At the time of randomization, serious imbalances in these covariates will be accounted for using a minimal sufficient balance approach¹⁰⁵. That is, at the time of randomization, an overall treatment imbalance and imbalance in each of the covariates is assessed. If no imbalances exceed the tolerated threshold, the subject is randomized according to the specified allocation ratio (1:1:1). If an unacceptable level of imbalance exists, the algorithm will determine whether the current allocation ratio improves or exacerbates the current imbalance and adjust the ratio accordingly. The detailed randomization scheme and source codes will be provided in the Randomization Plan document.

6.4 STUDY INTERVENTION COMPLIANCE

Compliance with study treatment will be centrally monitored.

7 STUDY INTERVENTION DISCONTINUATION AND SUBJECT DISCONTINUATION/WITHDRAWAL

7.1 DISCONTINUATION OF STUDY INTERVENTION

Discontinuation from tDCS and mCIMT intervention does not mean discontinuation from the study, and remaining study outcome assessments should be completed as indicated by the study protocol. If a clinically significant finding is identified (including, but not limited to changes from baseline) after enrollment, the investigator or qualified designee will determine if any change in subject management is needed. Any new clinically relevant finding will be reported as an adverse event (AE). An investigator may discontinue or withdraw a subject from study intervention for the following reasons:

- Pregnancy, but it is unlikely as woman of child-bearing potential will have urine pregnancy test to confirm or exclude the possibility of a pregnancy.
- Significant study intervention non-compliance, defined as missing >2 sessions out of 10 sessions and unable to make it up within the 2 week/14 days intervention period;
- If any adverse event (AE), laboratory abnormality, other medical condition or situation occurs such that continued participation in the study intervention would not be in the best interest of the subject.
- Disease progression (e.g., 4 points or more increases in the NIHSS score or recurrent stroke) which requires discontinuation of the study intervention.
- If a subject meets an exclusion criterion (either newly developed or not previously recognized) that precludes further study participation.
- Subject suffers another stroke, neurological or neuromuscular disease during the study period that may have an impact on motor recovery.

The reason for intervention discontinuation from the study will be recorded on the Case Report Form (CRF). The subject should continue to be followed and have all study assessments.

7.2 SUBJECT WITHDRAWAL FROM THE STUDY

Subjects are free to withdraw from participation in the study at any time upon request. The reason for subject withdrawal from the study will be recorded on the Case Report Form (CRF). Subjects who sign the informed consent form, and are randomized and receive the study intervention, and subsequently withdraw will not be replaced.

7.3 LOST TO FOLLOW-UP

A subject will be considered lost to follow-up if he or she fails to return for three scheduled visits and is unable to be contacted by the study site staff.

The following actions must be taken if a subject fails to return to the clinic for a required study visit:

- The site will attempt to contact the subject and reschedule the missed visit within 2 weeks and counsel the subject on the importance of maintaining the assigned visit schedule and ascertain if the subject wishes to and/or should continue in the study.
- Before a subject is deemed lost to follow-up, the investigator or designee will make every effort to regain contact with the subject (where possible, ≥ 3 telephone calls if necessary). These contact attempts should be documented in subject's study file.

8 STUDY ASSESSMENTS AND PROCEDURES

8.1 EFFICACY ASSESSMENTS

Primary Objectives (Efficacy Outcomes): To determine whether there is an overall intervention effect among 3 dosing groups (sham+mCIMT, 2 mA+mCIMT, and 4 mA+mCIMT) at day 15 after initiation of the intervention in the Fugl-Meyer Upper-Extremity (FM-UE) scale¹⁰⁶, a measure of motor impairment. FM-UE scale consists of a 33-item assessment which provides a global assessment of UE motor impairment. A rater observes 30 voluntary UE motions and 14 voluntary LE motions, 6 tendon tap responses, and provides an ordinal rating (2=near normal ability/response, 1=partial ability, 0=unable to perform/no response). FM-UE scale is a proven scale with excellent intra-rater reliability (0.99), inter-rater reliability (0.99), test-retest reliability (0.94 –0.99), and internal consistency (0.97).¹⁰⁷⁻¹⁰⁹

Secondary efficacy outcome measures include the Wolf-Motor-Function-Test (WMFT)¹¹⁰⁻¹¹², a measure of functional motor activity, and the Stroke-Impact-Scale (SIS)¹¹³, a measure of the quality of life at day 15 after initiation of the intervention. These efficacy outcomes will be collected at the baseline, day 15, day 45 and day 105. WMFT quantifies upper extremity (UE) motor ability through timed and functional tasks. It is a 17-item assessment providing a measure of UE functional ability. In this test, participants are timed as they complete 17 tasks that involve movements and interactions with objects (e.g., placing hand on table, picking up a soda can). These activities begin with those involving only shoulder movements and progress to those requiring distal control of fine motor movements. In addition, subject's movement will be assessed for meeting “**Essential Elements**” (specific elements) that must be accomplished in order for the task to be deemed complete” vs. “**Desired Elements**” which are other qualitative elements that should be included in the task but are not necessary for completion” (please refer to details in the Outcome Assessments MOP, located in the WebDCU Toolbox).¹¹⁵

SIS is a stroke-specific, self-report, health status measure assessing multidimensional stroke outcomes.^{113, 114} The current 3.0 version includes 59 items and assesses 8 domains: strength (4

items), hand function (5 items), Activities of Daily Living / Instrumental Activities of Daily Living (ADL/IADL, 10 items), mobility (9 items), communication (7 items), emotion (9 items), memory and thinking (7 items), and participation (8 items). The SIS hand function domain is a valid and reliable measure that is well aligned with TRANSPORT2 specific aims. It has face validity for clinical meaningfulness and this self-report measure of hand function corresponds well with other outcomes. While the specific effects of the Intervention are expected to influence the hand function domain the most, we also expect several non-specific effects on health status generally and the composite physical performance and social participation domains contained in the full SIS. This was true for the EXCITE trial which established the efficacy of mCIMT.

8.1.2 EXPLORATORY AIMS MEASURES

8.1.2.1 IMAGING MEASURES

We will determine **two imaging measures**: weighted corticospinal tract lesion load (**wCST-LL**) that be derived from the pre-intervention MRI and the **fractional anisotropy (FA) measure** that will be derived from the pre- and post-intervention MRI. These imaging measures support the exploratory aims/objectives outlined in section 3 above.

wCST-LL: Three MRI sequences (T1-weighted, T2-weighted, and FLAIR imaging) will be used to define and quantify the stroke lesion. A 3D map of this lesion will be overlaid onto a canonical corticospinal tract which was derived from a group of elderly healthy control subjects and exists in our lab as a representative map of the CST; (see [name] et al., 2015 for details). The overlap area between the lesion and the canonical CST will constitute our measure of wCST-LL. The weighting of the lesion load is related to the probabilistic nature of the tract and its geometric changes while it traverses from the cortex through the internal capsule into the brainstem. The **wCST-LL** is a continuous measure expressed in cubic centimeter (cc) with 2 decimals.

Corticospinal Tract - fractional anisotropy values (CST-FA): FA values are derived from an MRI sequence called diffusion tensor imaging (DTI). FA values will be determined in maps of the CST. Canonical maps of the CST (stretching from the posterior limb of the internal capsules to the lower brainstem) exist in our laboratory and have been previously described (see Zheng and [name], 2015 for details). FA is a measure of tract integrity or how well fibers are aligned in one direction in a tract. Values are between 0-1. Fractional anisotropy values tell us something about the direction of water flow. If the value is closer to 1, water flows along major fiber tracts in one particular directions, which means that the fibers are healthy and well aligned. Typically, on the side of the stroke, we might see a decrease in FA or water not only flowing in one direction but multiple directions, reflecting a degeneration of a fibers in a tract as an effect of the stroke. FA values derived from a template of the CST on the lesional and contralesional hemisphere will be determined in the pre-intervention MRI and post-intervention MRI and changes in these FA values will be correlated with behavioral changes within the three treatment groups as specified in the SAP.

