- **MRI:** MRIs will be done using equipment similar to that used for clinical MRI (either 1.5 or 3.0 T). The current revision of the US Food and Drug Administration guidelines (US Department of Health and Human Services, Food and Drug Administration, Center for Devices and Radiological Health, Guidance for the submission of premarket notifications for magnetic resonance diagnostic devices, Washington, DC. November 14, 1998) applies to this study. These guidelines state that magnetic resonance imaging systems with main static magnetic field strengths of 4.0 T (a measure of magnetic strength) and less, such as the ones used for this study, can qualify as non-significant risk devices. Because the MRI machine acts like a large magnet, it could move iron-containing objects in the MRI room during the examination, which could, in the process, possibly harm the subject. Magnetic media such as credit cards, etc. and watches near the coil may also be damaged. Precautions have been taken to prevent such an event from happening; loose metal objects, like key chains or paper clips, are not allowed in the MRI room. If a subject has a piece of metal in your body, such as a fragment in your eye, aneurysm clips, ear implants, spinal nerve stimulators, or a pacemaker, subject will not be allowed into the MRI room and cannot have an MRI. At times during the test, subject may be asked not to swallow for a while which can be uncomfortable.
- **TMS:** Single or paired-pulse TMS (not rTMS) will be used to determine the resting motor threshold as well as the amplitude of motor evoked potential on the affected and unaffected hemisphere. Although extremely rare, seizures have been described with single-pulse TMS, mainly in subjects who have a history of seizure. In some case reports, it was difficult to differentiate seizures from fainting or a convulsive syncope. The TMS coil makes noise, much like a loud pop when it produces its magnetic energy. Subject may or may not feel thumb twitch depending on the strength of the TMS pulse, but subject might also feel your facial muscles twitch slightly just around the eye. It is not painful. TMS can cause heating or movement of metallic objects in or near the head. In addition, the inactivation of pacemakers, medication pumps, cochlear prostheses and other implantable hardware may occur but subject with these metal implants is typically excluded from the study.

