3 OBJECTIVES AND ENDPOINTS

OBJECTIVES	ENDPOINTS	JUSTIFICATION FOR ENDPOINTS
------------	-----------	-----------------------------

Primary		
To determine whether there is an initial overall treatment effect among 3 dosing groups: • sham + mCIMT • 2 mA + mCIMT • 4 mA + mCIMT	FM-UE scale	FM-UE scale is the primary outcome and a measure of motor impairment
Efficacy is measured at day 15 after the initiation of the intervention.	WMFT time score	WMFT is a secondary outcome and a measure of functional motor activity
	SIS Hand Subscale	SIS Hand subscale is a secondary outcome and a measure of the quality of life
Secondary		
To confirm that the proposed intervention is safe, tolerable, and feasible to administer in a multi-site trial setting	Rate of adverse events	Safety needs to be monitored in a phase II study
	Visual Analog Scale	Visual Analog Scale measures tolerability
	Treatment completion rate	80% of treatment completion rate across sites without unexplained/unresolved variability is a measure of feasibility.
Tertiary/Exploratory		
To examine whether wCST-LL (structural assessment of integrity of descending motor tract) or MEPs (functional assessment of integrity of descending motor tract) or combination of both are correlated	wCST-LL (structural)	wCST-LL is a structural measure of integrity of descending motor tract using brain MRI that has shown promise in predicting motor outcomes.

with changes in FM-UE scale, and evaluate the utility of these measures as biomarkers for subject selection criteria in the future confirmatory Phase III study
	
MEPs (functional)
	
MEPs is a functional measure integrity of descending motor tract using TMS that has shown promise in predicting motor outcomes, but two of them have not been collected and compared in the same study.

To examine whether functional or structural changes in motor tracts correlate with changes in impairment and functional motor activity induced by the intervention.
	
Motor Evoked Potentials (MEPs) and Diffusion tensor imaging MRI.
	
MEPs can change in response to rehabilitation; Functional and structural aspects of motor tracts and the interaction between motor regions change after intervention. This change can be captured by comparing TMS and MRI measures before and after treatment

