In addition, with a sample size of 31 subjects per group, a two-sided type I error rate of 10%, and standard deviation of 7, if the true pattern of mean changes is 4.5, 9.0, and 9.0 for the sham, 2 mA, and 4 mA groups respectively, we would have 83% power to reject the null hypothesis. A 10% type I error rate was selected in consideration of the track record for safety in the intervention, the relative cost of committing a type I and type II error with respect to trial duration, subject utilization, and the remaining need for a subsequently planned Phase III trial should the current trial demonstrate promising results. Based on a conservative estimate from the EXCITE and VECTOR trial^{14, 19}, 8% of subjects are expected to complete less than 10 full sessions of tDCS + mCIMT in the specified 14 day time-window. Thus, the sample size is inflated for the cross-over in treatment effect using an inflation factor of $1/(1-0.08)^2$.¹¹⁷ In addition, up to 15% of subjects may be lost to follow-up prior to collection of the primary outcomes at the 3-month follow-up visit.

Therefore, an inflation of 115% is used to account for the missing samples in the ITT primary analysis. As a result, the final estimated sample size is 43 per group (or 129 subjects in total). Finally, considering the longitudinal nature of the design and adjustment for key covariates, the power will be maintained when using an auto-regressive (1) correlation structure regardless of the degree of correlation between FM-UE scale measured on proximal visits or the strength of the covariates as predictors. We elected not to further reduce the sample size both because a robust estimate of these quantities is not currently available, and to retain sufficient power to evaluate secondary hypotheses.

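### The protocol's FA-change analysis reads as one correlation per arm; a single arm-adjusted model would answer the exploratory objective with all 129 subjects

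*Combined protocol and SAP*

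**What the plan says.** Protocol section 8.1.2.1 (Imaging Measures) derives fractional anisotropy (FA) of the corticospinal tract from MRI before and after the intervention. It then states that "changes in these FA values will be correlated with behavioral changes within the three treatment groups", and the same sentence refers to the SAP for the specification.

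The objective this serves is in section 3, among the tertiary/exploratory aims: "To examine whether functional or structural changes in motor tracts correlate with changes in impairment and functional motor activity induced by the intervention". It asks one question about tract change and motor change and does not divide it by arm.

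Sections 9.4 and 9.4.6 send analysis detail to the SAP. The material reviewed held no SAP text, so this point concerns the protocol's wording only. The protocol gives no expected correlation, significance level, power, multiplicity rule or test of arm differences for the FA analysis.

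**The concern.** Read naturally, section 8.1.2.1 answers a question about the whole trial with three correlations, each using one third of the subjects. That creates two problems.

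- **Precision.** A correlation of moderate size can easily be missed in an arm of 43, yet would be found with high probability if all 129 subjects informed one estimate.
- **Interpretation.** Three separate results invite comparison. In a dose-selection trial, a significant correlation at one dose and a non-significant one at another is easily taken as a dose effect. Comparing p-values across arms does not test that. Arms with the same true correlation will often differ in significance by chance.

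**Working it through.** **Plan's own figures.** Section 9.2 powers only the FM-UE comparison. With means of 4.5, 9.0 and 9.0, SD 7, 31 per arm and a two-sided 10% level, the grand mean is 7.5 and the squared deviations sum to 9 + 2.25 + 2.25 = 13.5. The noncentrality is 31 × 13.5 / 49 = 8.54 on 2 and 90 degrees of freedom, giving 82.8% power (stated: 83%). For the sample size, 31 / 0.92² = 36.6, rounded up to 37; 37 × 1.15 = 42.55, so 43 per arm and 129 in total, as stated.

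**Inputs for the FA check.**
- From the plan: 43 per arm, 129 in total (section 9.2), and 1:1:1 allocation (section 6.1.2).
- Assumed: a common true r, varied because the plan gives none; a two-sided 5% level, with 10% as a variant; bivariate normality; complete FA pairs.
- Variant with missing pairs: 36 per arm, 108 in total. This applies in full the 15% loss that section 9.2 ties to the 3-month visit (43 × 0.85 = 36.6). It is pessimistic, because the second MRI is at day 15.

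**Standard error on the Fisher z scale.**
- One arm: 1/√(43 − 3) = 0.158.
- Arm-adjusted, two arm indicators: 1/√(129 − 3 − 2) = 0.090.
- Ratio: √(124/40) = 1.76.

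Adding baseline FM-UE costs one more degree of freedom: 1/√123 = 0.0902 instead of 0.0898.

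**Correlation detectable with 80% power at 5%**, tanh[(1.960 + 0.842) × SE]:
- 43 per arm: 0.42; arm-adjusted 129: 0.25.
- 36 per arm: 0.45; arm-adjusted 108: 0.27.

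**Power and disagreement.** With λ = atanh(r)/SE, power p = Φ(λ − z) + Φ(−λ − z). The chance that three arms with the same r do not all agree on significance is 1 − p³ − (1 − p)³ = 3p(1 − p).

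| Assumed r (5% level, 43/129) | One arm | Arm-adjusted | Ratio | Arms disagree |
|---|---|---|---|---|
| 0.1 | 10% | 20% | 0.48 | 26% |
| 0.2 | 25% | 62% | 0.40 | 56% |
| 0.3 | 50% | 93% | 0.54 | 75% |
| 0.4 | 76% | 99.7% | 0.77 | 54% |
| 0.5 | 94% | >99.9% | 0.94 | 18% |

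At 36/108 and r = 0.3, power is 43% against 88%, with 73% disagreement. At a 10% level with 43/129, one arm has 36%, 62%, 85% and 97% power for r of 0.2 to 0.5, against 73%, 96%, 99.9% and over 99.9%.

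**Test of a dose difference.** For r = 0.2 in one arm and 0.5 in another, 43 each, the difference on the z scale is 0.549 − 0.203 = 0.347 with SE √(2/40) = 0.224. Power at 5% is Φ(0.347/0.224 − 1.96) = 34%.

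**The case against.** The strongest objection is that separate testing is inferred. The sentence in section 8.1.2.1 does not say that arms are analysed separately, it would also fit a pooled within-group correlation close to the model proposed here, and it defers to the SAP. The section describes measures, not analyses. This stands: the point has to be put as a request to state or confirm the model.

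A reader might infer that per-arm analysis simply halves the power. The documents do not support a fixed figure, because they give no expected correlation. The ratio is 0.40 to 0.54 for r from 0.1 to 0.3, but 0.77 at r = 0.4 and 0.94 at r = 0.5. Likewise, 75% disagreement is the ceiling of 3p(1 − p), reached at p = 0.5, and not a typical value.

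A reader might also infer that the trial plans to claim a dose difference from which arms reach significance. Nothing in the protocol says so, and no decision rule is attached to the FA correlation.

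Field strength might look like a missing covariate, since section 2.3.1 allows scanners of "either 1.5 or 3.0 T". But FA change is a within-subject difference, and nothing in the documents shows that field strength confounds it.

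Finally, per-arm correlation has merits. It does not let a treatment shift in both FA and motor score create an association, and it does not impose one slope on sham and active arms. Arm adjustment keeps the first merit. The interaction term and per-arm estimates address the second, although the interaction test is weak.

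**Conclusion.** The concern holds as a point about the protocol's wording. Its natural reading gives each correlation one third of the subjects, for an objective that is not stated by arm, and raises the detectable correlation from about 0.25 to about 0.42. The power loss is large if the true correlation is about 0.3 or less and small at 0.5. Differing significance across arms would not be evidence of a dose difference at any of these values.

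This rests on an assumed common r, bivariate normality, a 5% level and complete FA pairs. Whether the SAP already specifies a pooled model could not be checked. The consequence is limited: the aim is exploratory and the primary FM-UE result is unaffected.

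**What to change.** State one linear model of motor change on FA change, adjusted for arm and baseline FM-UE (already a covariate in the primary model, section 9.4.2). The common slope answers the objective. Make an FA-change-by-arm term the only test of a dose difference, and note its low power. Report per-arm correlations with confidence intervals as description. Field strength may be added as an optional covariate. If the SAP already specifies such a model, align the sentence in section 8.1.2.1 with it.

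The cost is wording only, with no new scans, data or subjects. The downside is that the main estimate assumes a common slope, which the interaction term and the per-arm estimates check.
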